11.0 DATA ANALYSIS

Descriptive statistics (means, standard deviations, counts, and percentages) will be calculated for all variables. To evaluate if the primary efficacy variables differ by the three treatment groups (NuSmile PVSCC Signature Crowns, NuSmile ZR, and Strip composite crowns), ANOVA or Chi-square tests of association will be performed.

All subjects evaluated at the 6-month interval or beyond and subjects who have lost crowns or teeth will be considered for efficacy. All enrolled subjects defined here as those who have had at least one crown placed will be evaluated for safety. Any missing, unused or false data will be omitted from data analysis.

The primary efficacy variables in this trial are fit, positioning, proximal contact, marginal adaptation, color match, gingival status, crown retention, veneer/composite integrity, secondary caries, occlusal integrity, history of trauma, clinical pulp pathology, parents' esthetic satisfaction. Scores for efficacy variables will be summarized and displayed using descriptive statistics (means, standard deviations, counts, and percentages).

Inferential statistics will be used to detect significant differences in the primary efficacy variables by the treatment status at baseline and at 6, 12, 18, and 24 month follow-up. Statistical differences will be calculated using logistic regression models accounting for within cluster variance using generalized estimating equations (GEE).

Safety variables include Adverse Events and Unanticipated Adverse Device Effects. All subjects that have had crowns placed will be evaluated for safety. Descriptions of occurrences, incidence, severity and required treatments for Adverse Events and Unanticipated Adverse Device Effects Will be summarized and tabulated where appropriate.

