3. OBJECTIVES

The objective of this pilot study is to assess the clinical performance of NuSmile's Pre-Veneered Stainless Steel Crown – NuSmile Signature and NuSmile ZR compared with composite crowns - Success Essentials esthetic temps/strip crowns - at the Center for Pediatric Dentistry, Seattle, Washington.

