6. STUDY POPULATION

Ninety (90) subjects contributing to approximately 120 to 200 crowns on primary teeth will be recruited from the patient pool of the Center for Pediatric Dentistry who receive care under general anesthesia and enrolled into the study. A maximum of four crowns will be placed in any subject. It is estimated that it will take approximately 24 weeks to place all crowns and complete the baseline examination.

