7.4 Treatment Randomization

Restorations will be randomly allocated to a patient; all teeth in a single patient will be randomly allocated to receive one of the restoration treatments: 1) NuSmile Signature crowns (thirty patients in the intervention group 2) NuSmile ZR crowns (thirty patients in the intervention group and 3) and composite strip crowns (thirty patients in control group).

The randomization sequence will be created using STATA 12.0 (StataCorp, College Station, TX) statistical software using random block sizes, which are known only to the study statistician. The randomization list will be created and placed in the order determined above into opaque sealed envelopes prior to trial start. The envelopes will be kept in a secure place known only to the study coordinator, research assistants, and statistician.

Each patient will be assigned a random treatment when they arrive at the treatment appointment and after they have been determined eligible and have signed the consent form. The clinician will be told the treatment assignment immediately prior to the treatment appointment.

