APPENDIX 4: MARGINAL ADAPTATION

MARGINAL ADAPTATION	
A=	No discrepancies detected with explorer
B=	Detectable discrepancies but clinically acceptable
C=	Detectable discrepancies, not acceptable –replacement required

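### Section 11.0 names both ANOVA/chi-square and logistic GEE for the same primary variables without saying which governs; run on crowns, ANOVA/chi-square would ignore clustering within the child

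*Combined protocol and SAP*

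**What the plan says.** All of the analysis text is in Section 11.0 of the combined protocol and SAP.

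- The opening paragraph covers descriptive statistics and then the comparison of the primary efficacy variables across the three arms: "ANOVA or Chi-square tests of association will be performed". It gives no unit of analysis and no adjustment for clustering.
- A later paragraph covers inference on the same variables "by the treatment status at baseline and at 6, 12, 18, and 24 month follow-up". The method is: "Statistical differences will be calculated using logistic regression models accounting for within cluster variance using generalized estimating equations (GEE"). The cluster is not defined.
- On summaries: "Scores for efficacy variables will be summarized and displayed using descriptive statistics (means, standard deviations, counts, and percentages"). This covers all the primary variables, including those recorded as letter codes.

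The design behind these analyses is set out elsewhere. In Section 7.4, "all teeth in a single patient will be randomly allocated to receive one of the restoration treatments", so the child is the unit of randomisation. In Section 6, "A maximum of four crowns will be placed in any subject", with about 120 to 200 crowns expected from 90 children. Section 3 frames the comparison as "NuSmile Signature and NuSmile ZR compared with composite crowns". Appendices 1 to 14 give the scoring codes, and Section 10 gives the visit at which each item is assessed.

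**The concern.** Two methods are named for one set of variables and one comparison, and nothing ranks them. The first treats observations as independent. That is sound with one value per child. It is not sound if each crown is a row, because crowns in one mouth share the treatment, the oral environment, the habits and the general anaesthesia session. With treatment allocated by child, positive correlation makes the crown-level p-value too small on average, and crown types would be declared different too often.

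The second method can handle this, but only if the cluster is the child, which a reader must infer from Section 7.4. Two analysts who both follow Section 11.0 could therefore reach different conclusions on the same variable.

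A smaller gap adds to this. The model is logistic, but the plan does not say how scores with three or more codes enter it. In Appendix 4, grade B of marginal adaptation is "Detectable discrepancies but clinically acceptable", while grade C calls for replacement. A versus B+C and A+B versus C are therefore different outcomes.

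**Working it through.** **Inputs from the documents.** There are 3 x 30 = 90 children (Sections 5 and 7.4). With 120 to 200 crowns (Section 6), that is 120/90 = 1.33 to 200/90 = 2.22 crowns per child, at most 4.

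**Assumed, because the documents give no value.** Alpha 0.05, no true difference, 30 children per arm at the visit analysed, ICC 0.1 to 0.7, event rates of 5% and 20%, and the crown mixes below.

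**Formula.** With m crowns per child, the design effect is DE = 1 + (E[m²]/E[m] - 1) x ICC. An unadjusted three-arm chi-square (2 df, critical value 5.99) then has true size P(χ²₂ > 5.99/DE).

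| Crowns | Crowns per child (% of children) | E[m] | E[m²] | Ratio | DE at ICC 0.3 / 0.5 / 0.7 | Size at ICC 0.3 / 0.5 / 0.7 |
|---|---|---|---|---|---|---|
| 120 | 1-2 (67/33) | 1.33 | 2.00 | 1.50 | 1.15 / 1.25 / 1.35 | 7.4 / 9.1 / 10.9% |
| 120 | 1-4 (78/14/5/3) | 1.33 | 2.27 | 1.71 | 1.21 / 1.35 / 1.49 | 8.4 / 10.9 / 13.5% |
| 200 | 2-3 (78/22) | 2.22 | 5.10 | 2.30 | 1.39 / 1.65 / 1.91 | 11.6 / 16.3 / 20.8% |
| 200 | 1-4 (35/29/15/21) | 2.22 | 6.22 | 2.80 | 1.54 / 1.90 / 2.26 | 14.3 / 20.7 / 26.6% |

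**Simulation.** Beta-binomial, 40,000 trials per scenario, crown-level chi-square. Each cell gives the range over the two mixes.

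| Events | Crowns | ICC 0.3 | ICC 0.5 | ICC 0.7 |
|---|---|---|---|---|
| 20% | 120 | 7.4-8.4% | 9.0-10.7% | 10.9-13.0% |
| 20% | 200 | 11.7-13.9% | 16.4-20.6% | 20.9-27.2% |
| 5% | 120 | 5.5-6.3% | 7.0-8.3% | 8.4-10.0% |
| 5% | 200 | 10.0-12.5% | 14.7-18.2% | 19.8-24.3% |

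- At ICC 0.1 the size is 4.3-7.8% across mixes and event rates.
- Crown-level ANOVA at ICC 0.3-0.7 has size 7.1-26.7% for a continuous score, and 6.7-22.9% for three grades scored 1 to 3.
- With one value per child, the size is 3.4-5.3%.
- Child-clustered GEE at 20% events has size 3.9-6.6% with the ordinary robust Wald test, and 2.5-4.6% with a small-sample-corrected variance. At 5% events it is at most 1.3% and 0.7%, counting trials with an empty arm as non-rejections. An arm has no events in 17-47% of those trials at ICC 0.3-0.7.

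**Scales of the 13 primary variables.** Nine have three or more codes: fit 3, positioning 3, proximal contact 3, marginal adaptation 3, colour 5, gingival status 4, retention 6, veneer/composite integrity 5 and parents' satisfaction 4. Three are absent/present: secondary caries, trauma and clinical pulp pathology. Occlusal integrity has no scale in the appendices. 9 + 3 + 1 = 13. Parents' satisfaction is asked once about the child's teeth overall, so eight graded crown-level scores remain. Colour C1-C3 (type of discoloration) and retention C1-C4 (where cement remains) are nominal sub-codes, for which a mean or SD has no meaning.

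**Visits.** Section 10 schedules retention, veneer/composite integrity, secondary caries, trauma and clinical pulp pathology from month 3. These five have no baseline value to model, although Section 11.0 lists baseline for all the primary variables.

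**The case against.** The strongest reply is that the intended order is clear enough. ANOVA/chi-square appears in the opening paragraph beside descriptive statistics, as a test of association. A separate paragraph on inference names GEE with allowance for within-cluster variance. On that reading the sound method is already in the plan, and the study is a pilot with a convenience sample and no stated alpha or power. Much of this stands: the remedy is a clarification, and no stated figure is wrong. But the opening paragraph also says its tests evaluate whether the primary variables differ by arm, and nothing makes them subordinate. The pilot label does not remove the problem, because Section 11.0 plans to detect significant differences.

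A reader might infer that the trial's analysis ignores clustering, or that its error rate will be 20% or more. The documents support neither. The unit for ANOVA/chi-square is not stated, GEE is named, and the top figures need 200 crowns, unequal crowns per child and ICC 0.7 together. At ICC 0.1 with rare events the size can fall slightly below 5%.

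A reader might also infer that every graded score needs a binary cut-point. Section 11.0 says logistic, not binary. An ordinal logistic model needs no cut-point for ordered grades, and forced dichotomising discards information. What is missing is a statement of which model is meant.

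Finally, a compulsory small-sample correction would not be a clear gain. It makes an already conservative test more so for rare outcomes.

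**Conclusion.** The point holds in conditional form. Section 11.0 plans an unadjusted test and a cluster-adjusted model for the same primary variables, with no ranking, no unit for the first and no defined cluster for the second. If the unadjusted test is run on crowns, its false-positive rate is about 7-13% at 120 crowns and 12-27% at 200 crowns (20% events, ICC 0.3-0.7, alpha 0.05), about 4-8% at ICC 0.1, and not inflated with one value per child. The ICC, alpha, event rate and crown mix are all assumed. The direction for a positive ICC does not depend on them, apart from the test's own conservatism when events are rare. The figures take 30 children per arm at the visit analysed, so they do not cover attrition over the 24 to 30 months of follow-up. The missing rule for graded scores is a secondary gap in specification. This should be fixed before analysis.

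**What to change.** Amend Section 11.0 as follows.

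1. For crown-level variables, remove ANOVA/chi-square as a test. State that GEE with the randomised child as the cluster is the governing analysis. Fit it at each Section 11.0 visit where Section 10 schedules that variable, and report each NuSmile-versus-composite contrast.
2. Limit ANOVA/chi-square to items with one value per child, such as parents' satisfaction.
3. For each graded score, state whether it is modelled as ordinal or with a named binary split. Do not report means and SDs for the nominal sub-codes of colour (C1-C3) and retention (C1-C4); use counts and percentages.
4. Where an arm has no events, use a child-level exact test. A small-sample variance correction is optional, but the choice should be written down in advance.

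The cost is SAP wording and minor programming, with no new data. The price is precision: at ICC 0.3-0.7, confidence intervals are wider than unadjusted crown-level ones by a factor of √1.15 = 1.07 to √2.26 = 1.50, that is about 7-50%. That width reflects the information the design provides.

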10. STUDY ASSESSMENTS

Clinical Assessments will be done at baseline post crown placement; at months 3, 6, 12 and 18; and end of study visit occurring in range of 24 to 30 months from baseline.

Assessments and documentation required at each assessment interval:

• Photographs of selected teeth	Baseline
• Photographs of tooth preparations	Baseline and when possible
• Photographs of cemented crowns	Baseline
• Photographs of occlusal and frontal views	Baseline and when possible
• Assessment of fit	All intervals
• Assessment of positioning	All intervals
• Assessment of proximal contact	All intervals
• Assessment of marginal adaptation	All intervals
• Assessment of color: match , staining/color change	All intervals
• Assessment of time placement	Baseline
• Assessment of gingival status	All intervals
• Assessment of retention	3, 6, 12, 18 and 24 mo
• Assessment of veneer/composite integrity	3, 6, 12, 18 and 24 mo
• Assessment of secondary caries	3, 6, 12, 18 and 24 mo
• Assessment of trauma	3, 6, 12, 18 and 24 mo
• Assessment of clinical pulp pathology	3, 6, 12, 18 and 24 mo
• Assessment of radiographic pulp pathology	24 mo
• Assessment of tooth	All intervals
• Assessment of parents' esthetic satisfaction	All intervals (baseline at 3-month follow up)

Non-recall assessment to be done at the time of tooth/crown lost to study due to trauma. If this was to occur, the patient would be discontinued from study and the justification recorded.

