12.0 STUDY TERMINATION/SUBJECT WITHDRAWAL

12.1 Study Termination

This study may be terminated for the following reasons:

- Discovery of unforeseen risk that could jeopardize the dental/physical well-being of subjects
- Enrollment or recall rates those are not likely to produce sufficient data for evaluation of safety and efficacy
- Non-compliance with the study protocol, the Investigator Agreement, applicable FDA regulations or conditions of approval imposed by the reviewing IRB
- Withdrawal of IRB approval

In the event of study termination, the Principal Investigator will determine whether subjects are in need of additional treatment and/or follow-up observation as a result of participation in this trial.

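### Entry to the efficacy set depends on crown or tooth loss, and no rule says how a loss before month 6 counts in the by-visit inference

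*Combined protocol and SAP*

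**What the plan says.** The efficacy set is defined in section 11.0: "All subjects evaluated at the 6-month interval or beyond and subjects who have lost crowns or teeth will be considered for efficacy". There are two routes in, and the second has no limit on time or cause. The same section lists the outcomes: "The primary efficacy variables in this trial are fit, positioning, proximal contact, marginal adaptation, color match, gingival status, crown retention", followed by six more. Safety uses a wider set, everyone with at least one crown placed.

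Inference on these variables is planned "by the treatment status at baseline and at 6, 12, 18, and 24 month follow-up". Month 3 is not among those times, although section 10 schedules it ("Clinical Assessments will be done at baseline post crown placement; at months 3, 6, 12 and 18") and its list of assessments has retention first scored then. On gaps in the data, section 11.0 says: "Any missing, unused or false data will be omitted from data analysis".

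For trauma, section 10 says: "Non-recall assessment to be done at the time of tooth/crown lost to study due to trauma". It continues: "If this was to occur, the patient would be discontinued from study and the justification recorded". Appendix 8 has codes for a missing crown but no rule for later visits. The intention-to-treat statement in 7.5.4 covers only teeth that cannot take the allocated crown. Section 6.2 excludes teeth expected to be lost within one year, while the final visit falls at 24 to 30 months. Section 11.0 does not separate natural tooth loss from failure.

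**The concern.** Take two patients last seen at month 3. The one who has lost a crown is in the efficacy set; the one with intact crowns is not. Membership therefore depends on an outcome that the set is used to estimate. The second route was probably added to protect early failures, since a set of month-6 attenders alone would miss a patient discontinued after trauma. But it repairs only the numerator: intact patients who leave equally early stay out of the denominator.

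A second gap lies beside it. An early loser is admitted, but no rule says whether the loss counts at month 6 and later. With month 3 outside the inference, missing data omitted and traumatic losses followed by discontinuation, the loss may not reach the by-visit models. The first problem pushes the loss rate up and the second pushes it down, so the same data can give different rates under rules that the plan leaves open. Retention rates by arm are a main product of this pilot.

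**Working it through.** **Inputs.** From the documents: 30 patients per arm (section 5; 3 × 30 = 90 agrees with the stated total). There is no planned loss or drop-out rate to reproduce, so the rest is assumed:

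- p = 0.10, true patient-level loss by month 6
- s = share of those losses occurring by month 3 (0.5, varied from 0.25 to 0.75)
- d = permanent drop-out after month 3, meaning never seen at month 6 or later, unrelated to outcome (0.1 to 0.4)
- a = probability that an early loser has a month-6 record

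**Early losses counted.** The loss rate over the efficacy set as written is [ps + p(1−s)(1−d)] / [ps + (1−ps)(1−d)].

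| d | s = 0.5 | result |
|---|---|---|
| 0.1 | 0.095/0.905 | 10.5% |
| 0.2 | 0.090/0.810 | 11.1% |
| 0.3 | 0.085/0.715 | 11.9% |
| 0.4 | 0.080/0.620 | 12.9% |

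The inflation is 0.5 to 2.9 points. With s = 0.25 the rate runs from 10.2% to 11.5%, and with s = 0.75 from 10.7% to 14.3%, so the full range is about 0.2 to 4.3 points. At crown level, with two independent crowns per patient and s = 0.5, it is 10.4% to 12.5%. The one-arm standard error is √(0.1 × 0.9/30) = 5.5 points.

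**Early losses not carried forward.** The month-6 rate is [psa + p(1−s)(1−d)] / [psa + (1−ps)(1−d)]. With s = 0.5:

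- a = 0 (no early loser has a month-6 record): 0.05/0.95 = 5.3% for any d
- a = 0.5(1−d) (half are discontinued, the rest attend like others): 0.075/0.975 = 7.7%
- a = 1−d (all attend like others): 10.0%
- a = 1 (all attend): the same as the table, for example 11.1% at d = 0.2

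**Between arms, equal true rates, early losses counted, s = 0.5.** The odds are 0.095/0.81 = 0.117 at d = 0.1, 0.090/0.72 = 0.125 at 0.2, 0.085/0.63 = 0.135 at 0.3 and 0.080/0.54 = 0.148 at 0.4. The odds ratios for 10% against 20%, 30% and 40% drop-out are 1.07, 1.15 and 1.26. Equal drop-out, timing of losses and attendance give an odds ratio of 1.

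**Informative drop-out, early losses counted.** Suppose that 10% of intact patients leave but 40% of those with an unseen later loss leave. The rate is then (0.05 + 0.03)/(0.05 + 0.03 + 0.81) = 0.08/0.89 = 9.0%, so the direction reverses.

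**A direct count.** In an arm of 30, assume 4 early losers, 6 intact early leavers and no later losses. The month-6 loss rate is 0/20 = 0% if early losses are omitted, 4/24 = 16.7% over the efficacy set as written, and 4/30 = 13.3% over everyone crowned.

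**The case against.** The second route into the set is better than a plain completer rule, and it needs no cure if nobody leaves early with intact crowns. One visit at month 12, 18 or 24 is enough to enter, so 40% permanent drop-out is a severe assumption. At 10% to 20% drop-out with half of losses early, the inflation is only 0.5 to 1.1 points. All of this stands and limits the size of the point.

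A reader might infer that early losers have no analysed retention record at all. The documents do not support that. Section 11.0 calls for descriptive statistics on all variables with no limit on visit, so a loss scored at month 3 would appear there. The gap is in the by-visit inference.

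A reader might also take 5.3% as the expected result. It is an extreme. Section 10 discontinues patients only after loss due to trauma, and Appendix 8 lets a crown be scored as missing at a later visit, so a non-traumatic early loser who attends month 6 can be counted there.

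Nor does the plan predict poor recall. Section 12.1 lists, as one possible reason for termination, "Enrollment or recall rates those are not likely to produce sufficient data for evaluation of safety and efficacy". That is a contingency, not a forecast.

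Finally, one could ask only for a sentence that a recorded loss stays a failure. That closes the counting gap. But if losses are carried forward while intact leavers drop out of each visit's denominator, the month-6 rate is the one in the table above, so the inflation remains.

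**Conclusion.** The concern holds for crown retention, one of 13 primary efficacy variables. Outcome-dependent entry follows from the wording of section 11.0, and no other section repairs it. If early losses are counted and drop-out is unrelated to outcome, the inflation is about 0.2 to 4.3 points on a true 10%. This is smaller than the sampling error of one arm, and it can reverse if patients leave with unseen losses. If early losses miss the by-visit inference, loss can be understated, with 5.3% as the limit.

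It would go too far to conclude that the treatment comparison is biased. A spurious difference needs drop-out, timing of losses or attendance to differ by arm, and the documents give no sign that they will. The textual gap is certain. The size rests wholly on assumed inputs and was worked for month 6, mainly at patient level. The rules are worth fixing before data are seen, so that results cannot steer the choice.

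**What to change.** 1. Define the efficacy set as all randomised patients with at least one study crown placed, including a composite crown placed under 7.5.4, analysed in the randomised arm with every attended visit.
2. Add month 3 to the analysed time points for retention.
3. Count a recorded crown loss as a retention failure at that and every later time point, including a loss recorded at a non-recall assessment.
4. Keep intact crowns in the denominator up to the last attended visit, for example with an interval-based or time-to-loss estimate clustered on patient. State that this estimates cumulative loss, whereas the planned by-visit model estimates status at each visit.
5. State in advance whether loss of a tooth with its crown in place is an event or is censored.
6. Report drop-out before month 6 by arm, with a sensitivity analysis for patients lost while intact, from all intact to all failed.

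Under the assumptions above with s = 0.5, the interval estimate is 1 − 0.95 × (0.90/0.95) = 10.0% at any d, because non-informative drop-out cancels within the interval.

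The cost is analysis text, a little programming and one table; every assessment is already scheduled. There are downsides. Patients lost before month 3 add no retention information, and sparse intervals may have to be merged. The main analysis assumes non-informative drop-out: in the reversed case it gives 1 − 0.95 × (0.81/0.84) = 8.4% for a true 10%, slightly worse than the 9.0% under the present rule with early losses counted. The sensitivity range is wide. In an arm of 30 with s = 0.5 it runs from 2.85/30 = 9.5% to 5.70/30 = 19.0% at 10% drop-out, and from 2.7/30 = 9.0% to 8.4/30 = 28.0% at 20%.

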5. SAMPLE SIZE

As this is a pilot study, a sample size of 90 (30 in each arm) subjects will be chosen as a convenience sample. This is the number estimated to enroll in a 24 week period.

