6.2 Exclusion Criteria

- Medically compromising condition
- Teeth with proximal space closures of sufficient magnitude to preclude placement of crown
- Teeth with complete absence of facial or lingual walls following tooth preparation
- Teeth that are expected to be exfoliated/extracted within one year will not participate in the study
- Anterior crowding
- Occlusion class III

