7.5.4 Failure to Fit

Teeth randomized for treatment will be included in the study even if they cannot accommodate the crown and therefore a composite crown is placed instead (intention-to-treat principle). The investigator will keep record of the teeth for further adjustment in the analysis. The reason for the fitting failure will also be recorded (See Appendix 2). If the tooth needs to be extracted (not matching inclusion/exclusion criteria), it will be excluded from the trial.

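### The safety set requires a crown to have been placed, so a randomised child whose every study tooth is extracted or excluded after preparation drops out of the safety table

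*Combined protocol and SAP*

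**What the plan says.** Section 11.0 (Data Analysis) sets the safety population: "All enrolled subjects defined here as those who have had at least one crown placed will be evaluated for safety". It repeats the restriction later in the same section: "All subjects that have had crowns placed will be evaluated for safety". The efficacy population is defined differently: "All subjects evaluated at the 6-month interval or beyond and subjects who have lost crowns or teeth will be considered for efficacy".

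Allocation comes earlier. Section 7.4 states: "Each patient will be assigned a random treatment when they arrive at the treatment appointment and after they have been determined eligible". Section 4 describes the trial as non-blinded, and Section 7.4 has the clinician told the assignment just before treatment.

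Two provisions can remove a tooth after that point. Section 6.2 lists as an exclusion "Teeth with complete absence of facial or lingual walls following tooth preparation". Section 7.5.4 adds: "If the tooth needs to be extracted (not matching inclusion/exclusion criteria), it will be excluded from the trial". A misfit is handled the other way: "Teeth randomized for treatment will be included in the study even if they cannot accommodate the crown and therefore a composite crown is placed instead".

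Section 9 asks for adverse events to be documented for research subjects and does not require that a crown was placed.

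**The concern.** Exposure to the assigned treatment begins when the tooth is prepared, not when the crown is seated. Section 7.5.2 gives different preparations by arm: overall reduction of about 25-30% for Signature, 20-25% for ZR and 15-20% for strip crowns. The margins are about 1-2 mm subgingival in the two NuSmile arms, and at or above the gingival level in the strip arm.

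A safety set that depends on a crown having been placed therefore depends on something that happens after randomisation and after the arm-specific procedure has started. The plan keeps the milder operative failure (a crown that does not fit) and removes the tooth in the more serious one (extraction). If that leaves a child with no crown, the child disappears from the safety comparison. With an unblinded clinician judging exclusion, such losses could differ between arms, and the planned tables would not show it.

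**Working it through.** **1. Sequence for one child.**
- Consent and eligibility are confirmed, then the child is randomised on arrival (7.4).
- The study teeth are prepared by the method of the assigned arm (7.5.2).
- Each tooth then follows one of three routes. It receives its crown; it does not fit and receives a composite crown (7.5.4, tooth retained); or it is removed, through extraction (7.5.4) or wall loss judged after preparation (6.2).
- If at least one study tooth is crowned, the child is in the safety set and only the removed tooth is lost.
- If every study tooth is removed and no crown is placed, the child is outside the safety set (11.0).

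**2. Efficacy status of the child with no crown.** Section 7.5.4 takes the extracted tooth out of the trial. Section 11.0 admits to efficacy children who have lost teeth, which read literally can include this child. The text does not settle which governs.

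**3. Planned size.** Section 5 gives "a sample size of 90 (30 in each arm) subjects will be chosen as a convenience sample". Check: 3 × 30 = 90, which reproduces. There is no power calculation to check.

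**4. How many children could be one-crown children.** Inputs: 90 children, about 120 to 200 crowns, at most four per child (Section 6), and at least one needed for entry (6.1). Let n be the number with exactly one crown, the other 90 − n having two to four. For C crowns in total:

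n + 2(90 − n) ≤ C ≤ n + 4(90 − n), that is, 180 − n ≤ C ≤ 360 − 3n.

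- C = 120: n ≥ 180 − 120 = 60, and n ≤ (360 − 120)/3 = 80. Range 60 to 80.
- C = 200: 180 − n ≤ 200 holds for every n ≥ 0, and n ≤ (360 − 200)/3 = 53.3. Range 0 to 53.

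So children for whom loss of one tooth means loss from the safety set could be most of the sample or none of it.

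**5. How many would actually be dropped.** The documents give no rate of extraction or wall loss. For an assumed share q of children ending with no crown, the expected number is 90q and the chance of at least one is 1 − (1 − q)^90:

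| Assumed q | Expected of 90 | P(at least one of 90) |
|---|---|---|
| 1% | 0.9 | 0.60 |
| 2% | 1.8 | 0.84 |
| 5% | 4.5 | 0.99 |
| 10% | 9.0 | >0.99 |

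**6. Effect on a reported rate.** One child is 1/30 = 3.3 percentage points of an arm. As an assumed illustration, suppose two children in an arm of 30 each have an adverse event and are dropped, and 3 of the remaining 28 have one. The table shows 3/28 = 10.7%; with all 30 counted it would be 5/30 = 16.7%.

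**The case against.** The case against is substantial on scope. Section 7.5.4 excludes the tooth and not the child, and up to four crowns may be placed per child, so many children who lose a study tooth would stay in the safety set through another. A tooth that cannot take its assigned crown is kept with a composite crown and the reason is recorded, so misfit alone takes nobody out. Section 9 still has adverse events documented and escalated. This is also a pilot with a convenience sample and purely descriptive safety reporting, and defining a device safety set by receipt of the device is a recognisable choice.

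All of this narrows the point. It does not remove it, because Section 11.0 and not Section 9 decides who is tabulated. An event in a child with no crown could sit on a case report form and still be missing from the table and its denominator.

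A reader might infer more than the documents support:
- *That any child with an extracted study tooth is counted in neither safety nor efficacy.* Safety is lost only if no crown at all is placed, and the efficacy clause on lost teeth leaves that half open.
- *That such events go unrecorded.* Section 9 contradicts this.
- *That the situation must be common because at least 60 children have a single crown.* That minimum holds only at 120 crowns and is zero at 200. In either case it counts who could be affected, not how often it happens.
- *That preparation causes extractions, or does so unequally by arm.* Section 7.5.4 ties extraction to eligibility, and nothing attributes it to preparation rather than existing disease. The different reductions make an arm difference possible, not demonstrated.

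**Conclusion.** The concern holds in a narrow form. As written, the safety set leaves out randomised children whose study treatment was started but who end with no crown because every study tooth was extracted or excluded after preparation. This is a stated rule, given twice, and not a missing detail. Whether those children count for efficacy is unresolved between Sections 7.5.4 and 11.0.

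The size cannot be fixed from the documents. It is 3.3 points of a 30-child arm for each child dropped, with the number dropped unknown. The conclusion assumes that the 30 per arm refers to randomised children and that a tooth excluded under Section 6.2 does not receive a crown that would itself put the child in the safety set. The bounds on one-crown children also assume that all 90 children contribute one to four crowns.

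This deserves correction before analysis because the omission follows randomisation, could differ by arm, and is easily avoided.

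**What to change.** These are changes to analysis wording only; they do not touch how teeth are managed.

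1. In Section 11.0, define the safety set as all randomised children in whom preparation of at least one study tooth was begun, analysed by assigned arm. Replace both statements of the present rule.
2. Tabulate by assigned arm the operative extractions of study teeth and all other exclusions of study teeth after randomisation, with reasons, counted per tooth and per child.
3. Reconcile Section 7.5.4 with the efficacy definition in Section 11.0, so that the status of a child whose study teeth were all removed at operation is stated explicitly.

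The cost is revised SAP text, a small amount of extra tabulation, and possibly slightly less favourable safety counts. The planned sample size does not change; the safety denominator could reach the full 90 (30 per arm) if preparation is begun in every randomised child.
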